**Health and Justice: A Continuum of Care for HIV and SU for
Justice-Involved Young Adults (PHASE 2)**

NCT03369249

Study Protocol and Statistical Analysis Plan

(10/20/17)

**Health and Justice: A Continuum of Care for HIV and SU for Justice-involved Youth
(R01 DA 043122)**

**Principal Investigator:
[name]., Columbia University and New York State Psychiatric Institute**

Project Overview

Statement of Responsibility for developing and executing DSMP

The Principal Investigator accepts full responsibility for the development and execution of this Data and Safety Monitoring Plan.

Brief protocol description and study design

This protocol concerns the adaptation, efficacy-testing and implementation evaluation of a multi-component service delivery model (Link2CARE) that aims to increase HIV/STI testing and substance use (SU) screening; reduce HIV and SU risk; and increase linkage to HIV, STI and SU services in justice involved youth (JIY) who are enrolled in an alternative sentencing program (Brooklyn Justice Initiatives; BJI). We propose to adapt and integrate the following evidence-based strategies to create Link2CARE: (i) **Screening**: Offer an onsite rapid oral HIV test and STI urine test at intake into BJI and screen HIV risk behavior and SU; (ii) **Brief intervention**: use brief interventions (1-2 sessions) to reduce HIV risk and SU behavior and promote treatment/service readiness (*MOVE*¹ and *NYSBIRT*^{2,3}); (iii) **Linkage to HIV and SU care**: use a strengths-based patient navigator approach to mobilize JIY strengths and reduce barriers to treatment, while establishing formal relationships and referral protocols with service providers. We have initiated a partnership with BJI, which serves 9000 JIY annually, and Project STAY, a youth-focused, hospital- and community-based, health and HIV treatment program; Project STAY HIV testing outreach workers will be embedded into BJI to deliver Link2CARE. We will test the efficacy of Link2CARE in a randomized controlled trial among N=450 BJI-enrolled JIY (18-24 y.o.), randomized to either Link2CARE or standard of care (SOC) and conduct implementation evaluation to explore individual-, staff, and system-level influences on implementation of this new model to inform scale-up and dissemination. Youth will be assessed at baseline and 3-, 6-, and 12-months post-intervention. BJI and Project STAY staff will be assessed before launch of Link2CARE and 12 and 24 months later.

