Study aims and primary and secondary outcomes

The study has three aims.

1. Among 450 (18-24 y.o) JIY in BJI randomized to either Link2CARE or standard of care (SOC), to determine **the efficacy of Link2CARE** delivered by STAY staff embedded within BJI on (a) HIV outcomes: HIV testing/repeat testing; HIV risk behaviors; (b) STI outcomes: STI testing/repeat testing; linkage to care of JIY with STIs; (c) SU outcomes: SU screening; SU; linkage to care of JIY with SU/D; and (d) (exploratory) linkage to care of HIV+ youth and linkage to PrEP for (behaviorally) eligible HIV- youth.
2. To determine **the influence of theoretically-based mechanisms of change of Link2CARE** (e.g., predisposing characteristics, enabling resources, perceived need, organizational climate; staff attitudes) on the proposed HIV, STI and SU outcomes.
3. To describe Link2CARE implementation and elucidate the **system/organizational-, staff-, and youth-level factors that influence implementation (i.e. acceptability, sustainability, feasibility) of Link2CARE in an ASP** to develop a plan for dissemination and scale-up of Link2CARE in New York City

The study has the following primary, secondary, and exploratory outcomes (related to aim 1)

Domain 1 (primary outcomes: HIV outcomes): (a) total number of unprotected anal and vaginal sex occasions in past three months at 12 month FU; (b) acceptance of HIV testing at initial offering (y/n), (c) any HIV

testing between 6-month and 12-month FU (y/n).

Domain 2 (secondary outcomes: SU outcomes): (a) frequency of youth substance use in past 30 days at 3-, 6- and 12-month FUs; (b) number of youth referred to SU treatment at 3-, 6- and 12-month FUs; at (c) number of youth attending intake plus one treatment session at 3-, 6- and 12-month FUs.

Domain 3 (secondary outcomes: STI testing outcomes): (a) acceptance of STI testing at initial offering (y/n), (b) any STI testing between 6-month and 12-month follow up; (c) number of STI+ youth referred to STI treatment at 3, 6, and 12 months FUs; (d) number of STI+ youth attending ≥ 1 treatment appointment at 3, 6, 12 months FUs.

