Domain 4 (exploratory outcomes: HIV/PrEP linkage outcomes): (a) number of HIV+ youth referred to HIV treatment at 3, 6, and 12 months FUs, (b) number of HIV+ youth attending at least one treatment appointment at 3, 6, and 12 months FUs; (c) number of youth behaviorally PrEP eligible referred to PrEP/medical care at 3, 6, and 12 months FUs, (b) number of youth behaviorally PrEP eligible attending at least one HIV care appointment care at 3, 6, and 12 months FUs.

TRIAL MANAGEMENT

Study/data collection sites

Data will be collected at **Brooklyn Justice Initiative (BJI), run by Center for Court Innovation**. BJI is an alternative sentencing program (ASP) for JIY processed through Brooklyn Criminal Court. BJI aims to reduce re-offending and increase public safety; promote use of meaningful social services; provide rigorous compliance monitoring; and reduce criminal convictions and use of jail. Located in the Brooklyn Criminal Courthouse, BJI serves 9,000 youth/year; almost all (94%) are mandated to BJI for ≤ 15 days.

Study sample description

To address the study aims we will collect data from a sample of youth aged 18-24 who have been placed in BJI (sample 1), from a sample of HIV testing outreach staff (sample 2) and from staff at BJI (Sample 3).

Sample size and power

The total sample size of sample 1 will comprise N=472 youth currently enrolled at BJI: n=14 youth will serve on an advisory panel to provide feedback as MOVE and NYSBIRT are adapted; n=8 youth will pilot test the adapted Link2CARE protocols prior to the efficacy test of Link2CARE; and n=450 youth will be randomly assigned (1:1) to either Link2CARE or standard of care. Sample 2 will comprise N=2 Project STAY outreach workers who will be embedded at BJI and will deliver all elements of Link2CARE to youth. Sample 3 sample size is expected to be all 15 staff who work at BJI.

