DATA MANAGEMENT AND ANALYSIS

Data acquisition, entry and transmission

Study data will be collected in Phases 1 and 2. All Phase 1 and all baseline assessments (Phase 2) will be collected at BJI. Subsequent Phase 2 assessments will occur at BJI, in the participant’s home or at another agreed upon location. Note: BJI is not involved in survey administration, data entry and management, or data storage.

Phase 1: Advisory Panel data: Peer (n=14) and Staff (n=6) Advisory Panels will meet in a series of Panel workgroups during Phase 1 to provide feedback on the adaption of the SU and HIV interventions. Data from these Panel workgroups will be gathered in note form by work group facilitators and will not contain any participant identifying information. These data will be transcribed by research assistants and will be used between workgroups to inform adaptation of interventions.

Pilot data: n=8 youth who participate in a pilot of the SU and HIV protocols will complete paper-and-pencil process measures following the completion of the pilot which will be administered by human subject-trained research assistants (RAs). These research assistants will bring completed questionnaires to the research offices at NYSPI on the day of data collection. These data will be entered in an electronic database by human subject-trained research assistants. This database will be stored on password-protected computers in encrypted files. Researchers will retain the pilot process assessments until the completion of all project activities in Year Five when they will be destroyed following HIPAA standard document destruction services.

Phase 2: Substance use and HIV behavioral risk screen. Following randomization and baseline assessments, n=225 JIY randomized to Link2CARE will complete substance use and HIV behavioral risk screeners. Screening will take place at BJI in private rooms or other agreed upon location (for follow-up survey assessments). Data will be captured on encrypted, password protected computers, entered directly by human subjects-trained RA's into CiW using Sawtooth Software. Sawtooth Software allows for all standard question types, skip patterns, and data piping. Web-based data collection will **not** be used. Following interview completion, RAs will then transport interview data to NYSPI in the encrypted password protected computer, and immediately upload it upon return into the master database at NYSPI held on a secure server.

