HIV and STI testing: Following randomization and baseline assessment, all youth will be offered an HIV and an STI test for Chlamydia and gonorrhea; initial testing will take place onsite at BJI. All youth will also be offered HIV and STI testing at each follow-up interview (3m, 6m and 12m). **HIV testing** will be done using Oraquick advance rapid HIV test. Following brief pre-test counseling, an oral swab will be used to collect saliva to conduct HIV rapid test. Once conducted, the embedded Project STAY staff member (LINK2CARE condition) or human subjects-trained RA (standard of care) will provide results to the participant and HIV+ JIY will be immediately linked to care following Link2CARE linkage protocols. The Project STAY staff or RA will then place the swab in a closed Developer Solution vial, then back into the package. The entire package will be placed in a baggie. The baggie with the used test will be brought back to NYSPI by human-subjects trained RAs and turned in to the Project Director who will enter the results into a the project database at NYSPI that is held on a secure server. The baggie containing the used OraQuick test and materials will then be disposed of in the appropriate waste container. Staff (interviewers and office staff) will wear gloves when manipulating test materials. **STI testing** will occur by the collection and processing of the urine specimens using a Gen-probe APTIMA Urine Specimen Collection Kit for Male and Female Urine Specimens. The testing kits are provided and the urinalysis will be performed by the New York City Department of Health (NYCDOH) at no cost as part of an ongoing agreement with Project STAY. The client is instructed about how to provide the urine sample, and is sent to the bathroom by either the embedded Project STAY staff member (LINK2CARE condition) or human subjects-trained RA (standard of care). Upon return, the Project STAY staff member or RA packages the sample and arranges for pickup by the Department of Health's (DOH) Bureau of STD control. NYCDOH uses the third generation nucleic acid amplification test (NAAT), yielding qualitative testing results. Specimens will be collected and transferred into their respective specimen transport tubes. The transport solutions in these tubes release the rRNA targets and protect them from degradation during storage. When the APTIMA Combo 2 Assay is performed in the laboratory, the target rRNA molecules are isolated from specimens by the use of capture oligomers in a method called target capture. After the target capture steps are completed, the specimens are ready for amplification. The GEN-PROBE APTIMA Combo 2 Assay replicates a specific region of the 23S rRNA from CT and a specific region of the 16S rRNA from GC via DNA intermediates. A unique set of primers is used for each target molecule. Differences in the kinetic profiles of the CT and GC labeled probes allow for the differentiation of signal; kinetic profiles are derived from measurements of photon output during the detection read time. The chemiluminescent detection reaction for CT signal has very rapid kinetics and has the "flasher" kinetic type, while the detection reaction for GC signal is relatively slower and has the "glower" kinetic type. Assay results are determined by a cut-off based on the total RLU and the kinetic curve type. Written documentation of the test results will be obtained by the research office from the NYCDOH Microbiology laboratory within 7 days after the urine sample was delivered. The Project Director who will enter the results into a the project database at NYSPI that is held on a secure server Respondents randomized to Link2CARE who test positive will be informed by embedded Project STAY staff of their results and will immediately be linked to care by STAY staff following Link2CARE linkage protocols. Respondents randomized to SOC who test positive will be contacted by study staff using a succession of methods (telephone, registered letter, and, if refused or undelivered, regular mail). Participants will be informed that antibiotics are used to treat Chlamydia and Gonorrhea. We will counsel that all sex partners within the last 60 days should be evaluated and treated and to avoid sex until they and their partners have been treated for at least 7 days or 7 days after a single dose treatment. Specific referral procedures will be followed to maximize chances that participants will seek treatment.

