compared to the standard of care; all hypothesis tests will be conducted under the control of familywise error rate no greater than 0.05 level. The Holm step down procedure will be employed to adjust for multiple comparisons.

1. **Domain 1 (primary outcomes: HIV outcomes):** (a) total number of unprotected anal and vaginal sex occasions in past three months at 12 month FU; (b) acceptance of HIV testing at initial offering (y/n), (c) any HIV testing between 6-month and 12-month FU (y/n).
2. **Domain 2 (SU outcomes):** (a) frequency of youth substance use in past 30 days at 3-, 6- and 12-month FUs; (b) number of youth referred to SU treatment at 3-, 6- and 12-month FUs; at (c) number of youth attending intake plus one treatment session at 3-, 6- and 12-month FUs.
3. **Domain 3 (exploratory outcomes: HIV/PrEP linkage outcomes):** (a) number of HIV+ youth referred to HIV treatment at 3, 6, and 12 months FUs, (b) number of HIV+ youth attending at least one treatment appointment at 3, 6, and 12 months FUs; (c) number of youth behaviorally PrEP eligible referred to PrEP/medical care at 3, 6, and 12 months FUs, (b) number of youth behaviorally PrEP eligible attending at least one HIV care appointment care at 3, 6, and 12 months FUs.
4. **Domain 4 (STI testing outcomes):** a) acceptance of STI testing at initial offering (y/n), (b) any STI testing between 6-month and 12-month follow up; (c) number of STI+ youth referred to STI treatment at 3, 6, and 12 months FUs; (d) number of STI+ youth attending ≥ 1 treatment appointment at 3, 6, 12 months FUs.

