Analysis plan for Specific Aims 2 and 3. Descriptive statistics will be computed to quantify implementation at every step, by participant and by provider. Thus, we will be able to compute uptake of LINK2CARE, dose/intensity of intervention received, number of providers delivering each intervention, and other implementation parameters. Of note for Aim 2, which seeks to examine the proposed mechanisms of change of the intervention on HIV, STI and substance use outcomes, a given outcome (e.g. HIV/STI testing uptake, or PrEP uptake or reduced substance use) of this analysis will only be examined among those for whom it is relevant. For example, if a youth does not meet criteria for PrEP and as such is not offered PrEP, we would not include this youth in analyses of mechanisms of change of Link2CARE as they influence substance use or PrEP uptake as an outcome. We will examine the changes in specific outcomes (e.g. sexual behavior post-intervention) as a function of proposed theory-based intervention mediators (e.g. predisposing characteristics, enabling resources, perceived need for treatment/services). We will use structural equation models for these analyses. Structural equation modeling is preferred to multiple regression techniques because of the potential measurement error in our mediating variables and because of the possible feedback between dependent and mediating variables. We will test the model described in Figure 1 in the application, entering intervention condition as exogenous variables and the mediating factors included in Figure 1 as endogenous variables. Prior to conducting the structural analyses, however, we will examine the effects of the intervention on the putative mediating variables; a condition for inclusion in the equation will be a significant intervention effect on the potential mediators. Using standardized path coefficients, we will examine the relative associations of mediators to behavior change. We will also examine the path coefficient for the direct effect of the intervention after removing the effects of mediating constructs. For example, Link2CARE may have a more positive effect on acceptance of HIV (and STI) testing among JIY with greater perceived HIV risk, greater motivation to receive services, or positive HIV-testing history. Similarly, Link2CARE may have more positive effect on linkage outcomes when operating in an ASP that is more supportive of concepts perceived as innovative by both BIJ and STAY staff. Here, organizational culture would appear to modify Link2CARE's impact on youth service referral and engagement outcomes. We will examine the Lagrange Multiplier and Wald Tests to consider the deletion or inclusion of paths⁵; ultimately, however, deletion or inclusion of paths will be informed by theoretical underpinnings. Once the model is identified, we will test for group differences between intervention conditions in latent constructs and in the proposed paths between these constructs. This method will allow us to estimate the intervention effects on the constructs directly as well as their relationships to one another.⁶ We will use three goodness-of-fit indices: Bentler-Bonnet's Normed Fit Index, Bentler-Bonnet's Non-Normed Fit Index, and the Comparative Fit Index. We will also verify the root mean-square error of approximation (RMSEA) as an index of misfit. Well-fitting models will have fit indices of .90 or higher and $< .06$ for RMSEA.

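### SU screening and SU referral sit among the efficacy outcomes but mainly record delivery of Link2CARE, and the SU attendance hypothesis is framed within the referred subgroup

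*Combined protocol and SAP*

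**What the plan says.** The section on study aims and outcomes makes efficacy the subject of Aim 1 and lists, under it, "c) SU outcomes: SU screening; SU; linkage to care of JIY with SU/D". The outcome list that follows, repeated in the analysis plan for Specific Aim 1, gives Domain 2 three items: (a) substance use in the past 30 days, (b) "b) number of youth referred to SU treatment at 3-, 6- and 12-month FUs", and (c) attendance at intake and one session. SU screening is in neither list.

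The brief protocol description defines Link2CARE by three components. The first is to offer HIV and STI tests "at intake into BJI and screen HIV risk behavior and SU". The third is linkage through a navigator, including "establishing formal relationships and referral protocols with service providers". Under sample size and power, the two embedded outreach workers "will deliver all elements of Link2CARE to youth".

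Under data acquisition, after randomization and baseline assessment, "n=225 JIY randomized to Link2CARE will complete substance use and HIV behavioral risk screeners". By contrast, for HIV and STI testing, "all youth will be offered an HIV and an STI test for Chlamydia and gonorrhea". No SU screening or SU referral procedure is described for SOC.

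The hypotheses in the analysis plan for Specific Aim 1 name 30-day use and attendance as examples for the SU domain, but the attendance hypothesis is limited to youth who were referred. The analysis plan for Specific Aims 2 and 3 separately states that "we will be able to compute uptake of LINK2CARE, dose/intensity of intervention received".

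**The concern.** An efficacy outcome should be able to separate an intervention that helps youth from one that is delivered and changes nothing. HIV test acceptance can do this, because both arms receive the offer and the youth decides. SU screening cannot, because the protocol gives its screener in one arm only. SU referral does so poorly, because it depends heavily on what staff do, and the documents describe that activity only for Link2CARE.

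If either count were reported under Aim 1 as an SU effect, adherence to the protocol could be read as benefit. Limiting attendance to referred youth carries the problem forward: who is referred depends on arm, so the two referred groups are not protected by randomization.

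**Working it through.** **1. The plan's own figure.** The only power statement concerns the primary outcomes: 80% power for a standardized effect of 0.35 with 169 per group and Bonferroni correction over three outcomes. 450 × 0.75 = 337.5, stated as 338, or 169 per group. Power = Φ(0.35/√(2/169) − 2.394) = Φ(3.217 − 2.394) = Φ(0.823) = 0.795, so the figure reproduces. It does not bear on SU screening or referral, for which the documents give no rates. The 169 is used below as the expected number per arm at 12 months.

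**2. SU screening.** Setting the passages side by side is enough: screening is a component of Link2CARE, its workers deliver all components, and the screener is completed by that arm's 225 youth. For scale only, because the plan specifies no such test: if no SOC youth had a recorded screen, six screened youth out of 225 in Link2CARE would give a two-sided Fisher p = 2 × C(225,6)/C(450,6) = 0.030. Five would give 2 × C(225,5)/C(450,5) = 0.061. So 2.7% screened (6/225) would already be significant. If BJI screens youth as part of usual care, the gap is smaller; the documents are silent on this.

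**3. SU referral (2(b)).** All rates here are assumptions. Let the youth be identical in both arms, with a share p in need of SU care (20%, 40% or 60%). Staff refer a share q1 of those in need in Link2CARE (50% or 80%) and q0 in SOC (0.5%, 10%, 25% or 40%). The referral rates are P1 = p × q1 and P0 = p × q0. With n per arm, P̄ = (P1 + P0)/2 and two-sided 0.05:

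power = Φ{[P1 − P0 − 1.96 √(2P̄(1−P̄)/n)] / √[(P1(1−P1) + P0(1−P0))/n]}

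Example: p = 40%, q1 = 50%, q0 = 25%, n = 169 gives 20% vs 10%. The numerator is 0.10 − 1.96 × 0.0388 = 0.0239, the denominator is 0.0385, and power = Φ(0.62) = 0.73.

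Range over p = 20% to 60%, n = 169:

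| SOC refers, of those in need | Link2CARE refers 50% | Link2CARE refers 80% |
|---|---|---|
| 0.5% | 0.99 to 1.00 | 1.00 |
| 10% | 0.88 to 1.00 | 1.00 |
| 25% | 0.42 to 0.91 | 0.91 to 1.00 |
| 40% | 0.09 to 0.24 | 0.62 to 1.00 |

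No youth's substance use differs by arm in any cell. The result is driven by q1 − q0, a staff practice, and by an SOC rate that the documents do not give. The planned model is GEE with group-by-time terms and tests are under familywise control, so these two-proportion figures at an unadjusted 0.05 indicate scale only. They lean high, since any multiplicity adjustment lowers them.

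**4. Attendance among the referred.** Take p = 40%, q1 = 50%, q0 = 10%. The expected numbers referred are 169 × 0.40 × 0.50 = 33.8 in Link2CARE and 169 × 0.40 × 0.10 = 6.8 in SOC. A comparison among referred youth would then rest on about 34 against 7 of the 338 followed. The two groups would have been selected at different rates and perhaps by different criteria, so the bias could run either way. Compared over all randomized youth, 2(c) has no such selection.

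**The case against.** The strongest reply has four parts.

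- **No screening test exists.** SU screening appears only in the aim's wording. It has no definition, time point or model. This stands: the defect is a mismatch between Aim 1(c) and the outcome lists, not a biased test. A reader might infer that a significant screening result is built into the plan. The documents do not support that, because the comparison is never set up.
- **Referral is a fair question for a service-delivery model.** The protocol aims to increase screening and linkage, and whether more youth are referred than under SOC is a valid randomized comparison. This also stands, and is why 2(b) should remain a between-arm comparison. It still does not show that substance use or treatment attendance changed.
- **SOC may refer too.** BJI itself aims to promote use of social services, and a referral requires a youth with some SU need. A reader might infer that 2(b) favours Link2CARE almost regardless of what youth do. That is not shown. If SOC refers at close to the Link2CARE rate, the chance of significance falls to 0.09. Nor does a gap of about ten points in referral rates guarantee a likely win: exact Fisher power at 169 per arm is 0.52 for 30% vs 20% and 0.44 for 40% vs 30%.
- **Only secondary outcomes are touched.** True. Outcomes 2(a) and 2(c) sit beside 2(b), and the SU hypotheses given as examples already concern use and attendance. This limits the severity but does not repair the restriction of attendance to referred youth.

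**Conclusion.** The point holds in a limited form. Naming SU screening as an efficacy outcome is inconsistent with a screener that belongs to the intervention and is completed in one arm; this follows from the text and needs no assumed rates. Domain 2(b) is largely a service-delivery measure. Its tilt toward Link2CARE is strong if SOC referral is near zero (0.88 to 1.00) and can be weak if SOC already refers many (down to 0.09), under the assumed need and referral rates and the approximate test used here. The framing of attendance among referred youth conditions on a step that occurs after randomization and depends on arm. Outcome 2(a), and outcome 2(c) when taken over all randomized youth, are not affected. Severity is minor to moderate: no primary outcome and no sample-size figure changes.

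**What to change.** 1. In Aim 1(c), remove SU screening from the efficacy outcomes and report it with the uptake and dose measures in the analysis plan for Specific Aims 2 and 3.
2. In both Domain 2 lists, keep (b) as a between-arm comparison, labelled a service-delivery (process) outcome that does not by itself support SU efficacy.
3. State that the SU efficacy conclusion rests on 2(a) and 2(c), with 2(c) compared over all randomized youth.
4. In the Specific Aim 1 hypotheses, delete the clause limiting attendance to youth who were referred.

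The cost is wording only, with no new data, visits or participants. The real concession is that the sponsor can no longer offer referral as stand-alone evidence of SU efficacy; the counts and their comparison are still reported.

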Analysis plan for Specific Aim 1. Prior to conducting our multivariable analyses, we will examine study variables using descriptive statistics, testing for differences across demographic characteristics (e.g., race/ethnicity, age) using t-tests, ANOVAs, and Chi-squares, as appropriate. Systematic baseline differences are not expected; however, any parameters that differ across conditions at baseline will be included as covariates in subsequent models. We will calculate descriptive summary statistics corresponding to study variables at each follow-up (FU) to understand any temporal patterns, as well as compare the two groups in terms of average change from baseline to 12-months post-baseline. We will use the general framework of generalized linear models (GLM) to model the longitudinal outcome trajectories and GEE method to account for within-subject correlation across the four time points (baseline, 3-, 6-, and 12-months). Stratified randomization of participants to the groups based on their gender requires that the analysis also include gender as covariate. The general form of the analysis model will be $g(\mu) = \alpha_0 + \alpha_1 X + \beta I + \sum \gamma_i T_i + \sum \delta_i T_i I$, where g denotes the link function (identity for continuous outcome, logit for binary outcome and natural log for count outcomes) X represents the indicator of female (vs. male), I is the group indicator for Link2CARE (vs. SOC), and T_i is the indicator for time at 3-month, 6-month, and 12-month evaluation (vs. baseline) for $i=1, 2, \text{ and } 3$. The interaction coefficients δ_i are of interest, measuring the difference in the rate of change in outcome across the two treatment groups at each follow-up assessment. We will employ the above analytic approach to examine differences between youth in Link2CARE and in the SOC condition with respect to key study parameters within these four domains detailed below. Proposed hypotheses are that the experimental arm (Link2CARE) would have better outcomes (e.g. greater reduction on total number of unprotected anal and vaginal sex occasions in past three months from baseline to 12 month FU; greater increase in proportion of acceptance of HIV testing at initial offering; greater reduction on frequency of substance use in past 30 days at 3-, 6- and 12-month FUs; and of those referred to SU treatment, a greater number of youth attending intake plus one treatment session at 3-, 6- and 12-month FUs)

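### The STI referral and attendance outcomes are counts of STI-positive youth; they mix test uptake, positivity and linkage, so an arm difference cannot be read as a linkage effect

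*Combined protocol and SAP*

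**What the plan says.** Aim 1 (section on study aims and primary and secondary outcomes) promises efficacy on "b) STI outcomes: STI testing/repeat testing; linkage to care of JIY with STIs". The linkage half of that promise is served by two secondary outcomes, Domain 3(c), "c) number of STI+ youth referred to STI treatment at 3, 6, and 12 months FUs", and Domain 3(d), "d) number of STI+ youth attending ≥ 1 treatment appointment at 3, 6, 12 months FUs". The analysis plan for Specific Aim 1 repeats both as Domain 4. Neither place gives a denominator or a direction of benefit, or says whether the numbers are per visit or cumulative.

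The first two outcomes in the same domain are test uptake: "a) acceptance of STI testing at initial offering (y/n), (b) any STI testing between 6-month and 12-month follow up". The brief protocol description says the program "aims to increase HIV/STI testing and substance use (SU) screening; reduce HIV and SU risk; and increase linkage to HIV, STI and SU services", and the Aim 1 hypotheses include "greater reduction on total number of unprotected anal and vaginal sex occasions in past three months from baseline to 12 month FU".

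The HIV and STI testing section offers a urine test to every youth after randomization and baseline, and again at 3, 6 and 12 months. For the intervention arm it says "Respondents randomized to Link2CARE who test positive will be informed by embedded Project STAY staff of their results and will immediately be linked to care". Standard-of-care positives are contacted by study staff by telephone, then registered letter, then ordinary mail if the letter is refused or undelivered. The section closes with "Specific referral procedures will be followed to maximize chances that participants will seek treatment".

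**The concern.** A youth can enter the count only after accepting a test, testing positive, and being referred or attending. The program is designed to raise the first of these, lower the second through safer sex, and raise the third. More testing and better linkage push the count up, while prevention pushes it down. A higher count under Link2CARE could therefore mean more testing, more infection or better linkage, and a lower count could mean that prevention worked.

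What is at stake is the Aim 1(b) conclusion on linkage to STI care. As the plan is written, a difference in uptake or positivity could be reported as a linkage effect, and a real linkage gain could be hidden.

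**Working it through.** **The plan's own figure.** The documents give no sizing figure for these two outcomes. The only power statement covers the primary outcomes: 169 per group, standardized effect 0.35, Bonferroni over three tests, 80% power. It reproduces: 0.35 × √(169/2) = 3.217; 3.217 − 2.394 = 0.823; power 0.795. It does not bear on this point.

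**Inputs.** 450 youth randomized 1:1, so 225 per arm (Sample size and power). The documents give no uptake, positivity or attendance rates, so those below are assumptions.

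**Formula.** Expected count per arm = N × uptake × positivity among tested × P(attended | positive). Outcome (c) has the same form, with referral in place of attendance.

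| Scenario | Calculation | Count | Ratio to SOC |
|---|---|---|---|
| SOC | 225 × 0.60 × 0.10 × 0.60 | 8.1 | 1.00 |
| Uptake 80%, linkage unchanged | 225 × 0.80 × 0.10 × 0.60 | 10.8 | 1.33 |
| Attendance 80%, uptake unchanged | 225 × 0.60 × 0.10 × 0.80 | 10.8 | 1.33 |
| Positivity halved, linkage unchanged | 225 × 0.60 × 0.05 × 0.60 | 4.05 | 0.50 |
| Attendance 80%, positivity halved | 225 × 0.60 × 0.05 × 0.80 | 5.4 | 0.67 |
| Uptake 80%, attendance worse at 45% | 225 × 0.80 × 0.10 × 0.45 | 8.1 | 1.00 |

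The second and third rows cannot be told apart from the count. In the fifth row linkage is better and the count is lower. In the last row linkage is worse and the count is unchanged.

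**Range.** At an SOC positivity of 5% or 20% every count halves or doubles and the ratios stay the same. With 169 per arm (25% attrition at 12 months) the SOC, uptake-only and fifth-row counts are 6.08, 8.11 and 4.06, again with the same ratios.

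**Would a proportion among positives repair it?** That group forms after randomization through testing that may differ by arm, so the comparison is no longer a randomized one. It is also small. At an assumed 70% uptake, 225 × 0.70 × positivity of 5%, 10% or 20% gives about 8, 16 or 32 positives per arm. Power for 60% versus 80% attendance at two-sided 0.05 is then about 13%, 23% or 41%; 80% power would need 82 per arm.

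**Does other text supply what is missing?** The Aim 1 hypotheses condition on having been referred only for substance use treatment. The restriction of an outcome to youth for whom it is relevant appears under Aims 2 and 3 and is stated for the Aim 2 mechanism analyses. The Aim 1 model is fitted at participant level and does not say how a number of youth enters it. Coding each youth 0/1 over all randomized gives the same three-factor product.

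**The case against.** With 1:1 allocation, (d) amounts to the proportion of all randomized youth who were tested, found positive and attended care. That is a legitimate intention-to-treat composite, and number of youth may be shorthand for a participant-level binary outcome. Uptake is reported separately in Domain 3(a) and (b), and the plan promises descriptive summaries at each follow-up and of implementation at every step, so many of the parts would be visible. These are secondary outcomes with small numbers: 8.1 versus 10.8 is 3.6% versus 4.8% of 225, and z = 0.012 / √(2 × 0.042 × 0.958 / 225) = 0.63, which would support no claim either way.

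All of that stands, and it limits the severity. It does not supply a denominator or stop the counts from being read as linkage.

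Four stronger readings are tempting, and the documents do not support them:

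- A reader might infer that the counts say nothing about linkage. They carry some linkage information; they cannot separate it from uptake and positivity.
- A reader might infer that referral is fixed by protocol in both arms, so that (c) is only a count of detected infections. The testing section gives the arms different routes, and the standard-of-care route allows for refusal and non-delivery. Referral can fail and can differ by arm.
- A reader might infer that the plan predicts superiority on STI linkage. It applies one modelling approach to all four domains, but the hypotheses it lists as examples include none on STI referral or attendance.
- A reader might infer that prevention distorts every positive. The initial test directly follows randomization and baseline, so reduced risk can affect only infections found later. For the initial test the distortion comes from who accepts testing.

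**Conclusion.** The point holds in a limited form. Domain 3(c) and (d) cannot isolate linkage, and an arm difference on either has no fixed interpretation for the linkage part of Aim 1(b). Under the assumed rates, the attendance count rises by a third with no linkage change, or falls by a third while attendance improves from 60% to 80%. The sizes depend on assumed uptake, positivity and attendance; the identification problem does not, because it follows from the definitions. The halved positivity in the illustration applies only to follow-up infections. As the outcomes are secondary and the remedy is reporting and wording, this is a worthwhile low-cost correction and not a threat to the primary analysis.

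**What to change.** In both places where the domain is defined:

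1. Report by arm, at each follow-up, the numbers randomized, tested, positive, referred and attending at least one appointment, with denominators. Say whether the numbers are per visit or cumulative.
2. Express (c) and (d) as proportions of all randomized youth, labelled as a tested-positive-linked composite.
3. State that referral and attendance among detected positives are descriptive only, because that group forms after randomization through arm-dependent testing and is small.
4. State that no linkage efficacy claim will rest on the counts.

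Do not replace (d) with a composite that scores success as tested and negative, or positive and attended. At 60% uptake, 10% positivity and 60% attendance it equals 0.60 × (0.90 + 0.06) = 57.6%, and 0.54 / 0.576, about 94%, of its successes are test-negative youth. Raising attendance to 80% moves it only to 0.60 × (0.90 + 0.08) = 58.8%. With 80% uptake and no attendance at all it is 0.80 × 0.90 = 72%, above the 60% reached by perfect linkage at 60% uptake. It would mostly re-measure Domain 3(a) and (b).

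The cost is SAP wording and a table from data already planned. The trial gives up a confirmatory STI linkage claim, which these outcomes could not support in any case.
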